8.2 Discussion of Study Design

The study population consists of subjects who completed Study HZNP-ACT-302; this population was well-defined and consistent with the expected target population for whom ACTIMMUNE will be indicated (pediatric and young adult subjects with a FA functional stage of >1 to <5).

8.3 Selection of Study Population

8.3.1 Inclusion Criteria

Eligible subjects must meet all of the following criteria:

1. Written informed consent and child assent, if applicable.
2. Completed 26 weeks of treatment and the Week 28 Follow-Up Visit in Study HZNP-ACT-302.
3. If female, the subject is not pregnant or lactating or intending to become pregnant during the study, or within 30 days after the last dose of study drug. Female subjects of child-bearing potential must have a negative urine pregnancy test result at Week 26 of Study HZNP-ACT-302 and agree to use a reliable method of contraception throughout the study and for 30 days after the last dose of study drug.

8.3.2 Exclusion Criteria

Subjects will be ineligible if, in the opinion of the Investigator, they have a concomitant disease or condition that could interfere with the conduct of the study or potentially put the subject at unacceptable risk.

8.3.3 Removal of Subjects from Therapy or Assessment

All subjects are free to withdraw from study participation at any time, for any reason, and without prejudice to their further medical care. In addition, the investigator may terminate a subject from the study at any time. The primary reason for discontinuation should be recorded on the eCRF using one of the following categories:

- Adverse event. The subject experiences an adverse event that imposes an unacceptable risk to the subject's health, or the subject is unwilling to continue because of an adverse event.
- Lack of therapeutic effect. The investigator has determined that study drug administration is not benefitting the subject, and continued participation poses an unacceptable risk to the subject.
- Inclusion/exclusion criteria violation. The investigator discovers that the subject did not meet all of the inclusion/exclusion criteria after study enrollment.
- Lost to follow-up. The subject does not return to the clinic for scheduled assessments, and does not respond to the site's attempts to contact the subject.
- Voluntary withdrawal. The subject (or subject's legally acceptable representative) wishes to withdraw from the study. The clinical site should attempt to determine the underlying reason for the voluntary withdrawal and document it on the eCRF; if the underlying reason is documented as an adverse event or lack of efficacy, the category of withdrawal should be marked in the corresponding category and not as voluntary withdrawal.
- Study termination. The Sponsor, IRB, or regulatory agency terminates the study.
- Pregnancy.

Following premature withdrawal from the study, the subject or his/her legally acceptable representative will be contacted by telephone to enquire about any adverse events and concomitant medication use.

Discontinued or withdrawn subjects will not be replaced. Subject identification numbers are unique and will not be reassigned.

8.4 Treatments

8.4.1 Treatments Administered

All subjects will receive ACTIMMUNE. The planned treatment duration is open-ended, and treatment will continue until ACTIMMUNE is commercially available for the treatment of FA in the US or until the Sponsor discontinues development for this indication.

8.4.1.1 Dose Adjustment Guidelines

Subjects will receive SC doses of ACTIMMUNE TIW at home. The initial dose of ACTIMMUNE will be determined by the investigator for each subject, provided that the initial dose does not exceed the maximum tolerated dose in HZNP-ACT-302. The investigator may subsequently adjust the dose for any subject if deemed clinically appropriate, provided that the dose does not exceed 100 µg/m².

8.4.2 Identity of Investigational Products

8.4.2.1 ACTIMMUNE

ACTIMMUNE is a single-chain polypeptide containing 140 amino acids with a molecular weight of approximately 16,465 Daltons. ACTIMMUNE differs from natural human IFN- γ by the substitution of an additional N-terminal methionine, deletion/loss of seven amino acids and lack of glycosylation.

The commercial formulation of ACTIMMUNE is a sterile, clear, colorless solution filled in a single-use vial for SC injection. Each 0.5 mL of ACTIMMUNE contains: 100 µg (2 million international units [IU]) of IFN- γ 1b formulated in 20 mg mannitol, 0.37 mg disodium succinate hexahydrate, 0.14 mg succinic acid, 0.05 mg polysorbate 20, and sterile water for injection.

The Sponsor will provide unlabeled, commercial ACTIMMUNE to CSM. The commercial formulation will be utilized, with each unlabeled vial containing ACTIMMUNE in a concentration of 200 µg/mL. Each vial permits the extraction of up to 0.5 mL of ACTIMMUNE with additional volume to facilitate solution withdrawal. The study drug vials will be shipped to CSM, who will be responsible for labeling of the vials in accordance with regulatory guidelines (see [Section 8.4.3](#)) and assembling vials into kits. If a subject requires two vials per dose, the same volume should be removed from each vial and delivered in individual syringes. For example, if the dose should be 0.8 mL, then 0.4 mL should be withdrawn from each vial into separate syringes and two injections given.

8.4.3 Labeling

CSM will label the ACTIMMUNE vials, assemble the study drug into kits, and ship kits to the study sites as well as provide direct-to-subject shipments.

Labels on all vials of study drug and study drug kits will clearly indicate the study number, Sponsor's name and location, storage conditions, and appropriate precautionary labeling required

by US Federal law. Kit labels will also include the unique subject ID. Dosing instructions will be provided separately to the subject/caregiver.

8.4.4 Storage

Study drug kits are to be stored in a 2°C to 8°C (36°F to 46°F) refrigerator at the site, and subjects and their caregivers will be instructed to store all study drug in their home refrigerators.

At the clinic, all study medications must be stored in a secure area with limited access, and a daily temperature log of the drug storage area will be maintained every working day; significant deviations from the specified temperature range will be reported as protocol deviations.

Vials must be placed in a 2°C to 8°C (36°F to 46°F) refrigerator immediately upon receipt to ensure optimal retention of physical and biochemical integrity. The vials must not be frozen. Excessive or vigorous agitation should be avoided. Exposure of vials to temperatures greater than 25°C (77°F) should be strictly avoided. The sponsor should be contacted for disposition instructions for vials left at room temperature (>8°C) for a total time exceeding 8 hours. Vials should not be used beyond the expiration date.

8.4.5 Study Drug Quality Issues

ACTIMMUNE is a sterile, clear, colorless solution. If any vials of study drug are not colorless or contain particulate matter, study drug MUST NOT be administered. In the event that any of the vials stored at home are considered suspect by the subject/caregiver, the clinic is to be notified immediately for instructions regarding dosing and possible re-supply. The clinic will notify the Sponsor and Med Communications, Inc. of any product complaints.

8.4.6 Drug Accountability

The Principal Investigator at each site is responsible for the control of all study medication. The site must maintain adequate records of the receipt and disposition of all study medication shipped to the study center. Records will include receipt dates, quantities received, quantities dispensed, quantities returned or destroyed, and the ID numbers of the subjects who received study medication.

All empty, partially empty, and full vials of study drug must be retained by the study center under locked storage, until drug accountability has been completed. Periodically throughout the study and at the conclusion of the study, inventory checks and accountability of study materials will be conducted by the Sponsor or the Sponsor's representative. Once accountability is completed, the Sponsor or its representative will authorize the return of study medication (all used, partially used, and unused vials) to CSM. The completed Drug Accountability and Drug Return/Destruction Record(s) will be returned to the Sponsor. The investigator's copy of the Drug Accountability and Drug Return/Destruction Record(s) must document accurately the return of all study drug supplies. Records will also include disposition dates and quantities returned to the designated facility.

In addition, subjects or their caregivers can return biohazard containers supplied by study staff with all used syringes and needles from the study to study staff at the follow-up visit(s). Study staff will dispose of these containers appropriately.

8.4.7 Study Drug Administration and Timing of Dose for each Subject

8.4.7.1 Description of Clinical Supplies

CSM will supply study drug kits and packages containing ancillary supplies for dosing (i.e., syringes, alcohol swabs, gauze pads, bandages, and biohazard containers for safe storage of used needles and syringes) to the study sites as well as the direct-to-subject shipments.

8.4.7.2 Determination of Dose Volume

The volume of study drug to be administered will be determined by the site and will be based on the subject's body surface area (BSA). The BSA will be calculated using the Mosteller [Mosteller, 1987] formula:

$$BSA (m^2) = \sqrt{\frac{Height (in) * Weight (lb)}{3131}}$$

Given that each 0.5 mL of study drug solution contains 100 µg IFN- γ 1b (0.005 mL/µg), the following calculation will be used to determine the volume of study drug to be administered.

$$\text{Dose } (\mu\text{g}/\text{m}^2) \times \text{ BSA } \times 0.005 \text{ mL}/\mu\text{g} = \text{ ___ mL to be dosed}$$

For example, a subject who is 62 inches tall and weighs 100 pounds will have a BSA of 1.41 m². If the dose is 100 µg/m², the subject will receive **0.71 mL** of study drug.

$$100 \mu\text{g}/\text{m}^2 \times 1.41 \text{ m}^2 \times 0.005 \text{ mL}/\mu\text{g} = 0.705 \text{ mL, rounded to } \mathbf{0.71 \text{ mL}} \text{ of study drug}$$

8.4.7.3 Details Concerning Timing and Dose Administration

All doses of study drug will be administered by SC injection. Subjects and/or their caregivers will be instructed on their individualized dosing volume and proper dosing techniques; they will also be instructed to administer the study drug on the right and left deltoid, anterior thigh, and upper and lower abdomen and to rotate the injection sites.

Subjects or their caregivers will also be instructed in safe handling and storage of used syringes and needles. The clinical staff will demonstrate proper technique for withdrawing the appropriate volume of study drug from the vial. If two vials are needed to achieve the dose, an equal volume should be removed from each vial. For example, if the dose should be 0.8 mL, then 0.4 mL should be withdrawn from each vial into separate syringes and two injections given. The injection site will be cleaned with an alcohol swab and allowed to air dry. About an inch of skin and fat tissue will be pinched between the thumb and forefinger, the needle will be inserted all the way into the pinched skin, and the entire volume of study drug will be injected under the skin.

Subjects and their caregivers will be instructed to administer study drug on an outpatient basis TIW (e.g., a dosing schedule of Monday, Wednesday and Friday or Tuesday, Thursday, and Saturday) for the duration of the study.

At each clinic visit, subjects and/or their caregivers will be dispensed a 3-month supply of study drug, and an additional 3-month supply will be directly shipped to the subjects' home in between the required 6-month clinic visits. If direct shipments are not feasible, subjects will return to the clinic every three months to obtain study drug. At all post-Baseline clinic visits, subjects and/or their caregivers will return all unused kits and study drug vials.

8.4.8 Method of Assigning Subjects to Treatment

All subjects will receive ACTIMMUNE in this open-label extension study.

Subjects will maintain the unique 6-digit subject ID number assigned in Study HZNP-ACT-301 and carried through to Study HZNP-ACT-302; the first three digits are the site number and the last three digits are the sequential number assigned by the site to subjects who consented to the double-blind study beginning with 001. So for example, the first subject consented at site 222 in Study HZNP-ACT-301 would have been assigned subject ID 222001.

8.4.9 Blinding

This is an open-label safety extension study.

8.4.10 Concomitant Therapy and Restricted Medications

Concomitant medication use will be monitored throughout the study. No specific concomitant medications are restricted.

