Patients with FA have frataxin protein levels in peripheral tissues that range from 2-30% of control levels. The level of frataxin protein correlates with age of onset and inversely with the length of the GAA repeat. In carriers, who do not develop symptoms of FA, frataxin protein levels range from 30-80% of control levels [Deutsch et al, 2010]. The lack of symptoms observed in carriers suggests that restoration of frataxin levels in patients to those observed in carriers may lead to substantial improvement of symptoms.

At present, no therapy is approved for use in FA [Corben et al, 2014; Delatycki et al, 2014]. Many of the therapies being developed are designed to increase levels of frataxin, either by reversal of its transcriptional depression or by other means [Arpa et al, 2014; Lynch et al, 2010; Lynch et al, 2012]. Frataxin-depleted cells have an increased sensitivity to oxidative stress. Subtype-selective histone deacetylase (HDAC) inhibition has been successful *in vitro* at increasing levels of transcription of frataxin, and is beginning early stage trials in humans [Rai et al, 2008; Sandi et al, 2011]. Erythropoietin and its derivatives raise frataxin levels in peripheral tissues by non-transcriptional means, but the effect has been too small to observe efficacy in human trials [Boesch et al, 2014; Mariotti et al, 2012].

IFN- γ , a protein produced by the immune system in response to infections, increases both frataxin messenger RNA (mRNA) and protein levels in a variety of different cell types, including cell lines derived from FA patients. In addition, an FA mouse model treated with subcutaneous (SC) injections of IFN- γ for 14 weeks showed improvements in motor coordination, an effect

that was mirrored by accumulation of frataxin protein in the DRG tissue in these mice [Tomassini et al, 2012]. Its mechanism of action is as a transcriptional activator of multiple genes. From a therapeutic perspective, ACTIMMUNE is approved for use in the US in patients with CGD and SMO (see prescribing information in [Section 16.2](#)), and has been investigated in other conditions, including oncology, infectious diseases, and inflammatory disorders.

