16.2 Approved US Labeling for ACTIMMUNE

Interferon γ -1b was approved in 1990 in the US under the trade name ACTIMMUNE as a treatment to reduce the frequency and severity of serious infections associated with CGD, an inherited disorder characterized by deficient phagocyte oxidative metabolism (BLA 103836, approved for orphan indication). In February 2000, approval was obtained to market the product in SMO, a rare (and often fatal) bone disorder (BLA 103836/1001, approved for orphan indication).

The current version of the approved US labeling (02 June 2015) is included in this appendix; any subsequent updates to the labeling can be found at

http://actimmune.com/pdf/10889_Actimmune-PI_8_5x11.pdf

HIGHLIGHTS OF PRESCRIBING INFORMATION

These highlights do not include all the information needed to use ACTIMMUNE® safely and effectively. See full prescribing information for ACTIMMUNE.

ACTIMMUNE® (interferon gamma-1b) injection, for subcutaneous use.
Initial U.S. Approval: 1990

INDICATIONS AND USAGE

ACTIMMUNE is an interferon gamma indicated for:

- Reducing the frequency and severity of serious infections associated with Chronic Granulomatous Disease (CGD) (1)
- Delaying time to disease progression in patients with severe, malignant osteopetrosis (SMO) (1)

DOSAGE AND ADMINISTRATION

- For subcutaneous use only (2.1)

- The recommended dose is 50 mcg/m² for patients whose body surface area is greater than 0.5 m² and 1.5 mcg/kg/dose for patients whose body surface area is equal to or less than 0.5 m² three times weekly. (2.1)
- Monitor hematology, blood chemistries and urinalysis prior to the beginning of treatment and at 3-month intervals. (2.1)
- If severe reactions occur, reduce dose by 50 percent or discontinue therapy until the adverse reaction abates. (2.3)

DOSAGE FORMS AND STRENGTHS

Injection: 100 mcg (2 million International Units) of Interferon gamma-1b in 0.5 mL solution in a single use vial. (3)

CONTRAINDICATIONS

Known hypersensitivity to interferon gamma, *E. coli* derived products, or any component of the product (4)

WARNINGS AND PRECAUTIONS

- Cardiovascular Disorders:* Pre-existing cardiac conditions may be exacerbated. (5.1)

FULL PRESCRIBING INFORMATION: CONTENTS*

1	INDICATIONS AND USAGE
2	DOSAGE AND ADMINISTRATION
2.1	Dosing Information
2.2	Important Administration Instructions
2.3	Dose Modification
3	DOSAGE FORMS AND STRENGTHS
4	CONTRAINDICATIONS
5	WARNINGS AND PRECAUTIONS
5.1	Cardiovascular Disorders
5.2	Neurologic Disorders

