5.3	Bone Marrow Toxicity
5.4	Hepatic Toxicity
5.5	Hypersensitivity Reactions
5.6	Renal Toxicity
5.7	Allergic Reactions to Natural Rubber
6	ADVERSE REACTIONS
6.1	Clinical Trials Experience
6.2	Postmarketing Experience
6.3	Immunogenicity
7	DRUG INTERACTIONS
7.1	Myelosuppressive Agents
7.2	Drugs with Neurotoxic, Hemotoxic or Cardiotoxic Effects
7.3	Immunological Preparations

- Neurologic Disorders:* Reduce dose or discontinue if decreased mental status, gait disturbance, dizziness occur. (5.2)
- Bone Marrow Toxicity:* Monitor for neutropenia and thrombocytopenia particularly when administering ACTIMMUNE in combination with other potentially myelosuppressive agents. (5.3)
- Hepatic Toxicity:* Reduce dose or discontinue to reverse severe elevations of aspartate transaminase (AST) and/or alanine transaminase (ALT); monitor liver function monthly in patients less than 1 year old. (5.4)
- Hypersensitivity Reactions:* If serious hypersensitivity reactions occur, discontinue and institute appropriate medical therapy. (5.5)
- Renal Toxicity:* Monitor renal function regularly when administering ACTIMMUNE to patients with severe renal insufficiency (5.6)

DRUG INTERACTIONS

- Concomitant use of drugs with neurotoxic, hemotoxic or cardiotoxic effects may increase the toxicity of interferons. (7.2)
- Avoid simultaneous administration of ACTIMMUNE with other heterologous serum protein or immunological preparations (e.g., vaccines). (7.3)

ADVERSE REACTIONS

Common adverse reactions (incidence rate 2% or greater) for ACTIMMUNE include fever, headache, rash, chills, injection site erythema or tenderness, fatigue, diarrhea. (6)

To report SUSPECTED ADVERSE REACTIONS, contact Horizon Pharma USA, Inc. at [name] or FDA at [name] or www.fda.gov/medwatch.

USE IN SPECIFIC POPULATIONS

Based on animal data, may cause fetal harm. (8.1)

See 17 for PATIENT COUNSELING INFORMATION and FDA-approved patient labeling.

Revised: 8/2015

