7.3 Immunological Preparations

Simultaneous administration of ACTIMMUNE with other heterologous serum protein preparations or immunological preparations (e.g., vaccines) should be avoided due to the risk of an unexpected, or amplified, immune response.

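### Section 8.4.10 restricts no concomitant medication, although the label appended to the protocol advises against giving the drug simultaneously with vaccines, other immunological preparations or heterologous serum proteins

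*Protocol*

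**What the plan says.** Protocol Section 8.4.10 consists of two sentences. The first is "Concomitant medication use will be monitored throughout the study"; the second is "No specific concomitant medications are restricted". No drug class is named and the label is not mentioned.

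Appendix 16.2 reproduces the approved US labeling, which "is included in this appendix; any subsequent updates to the labeling can be found at" a web address. Section 7.3 of that label reads "Simultaneous administration of ACTIMMUNE with other heterologous serum protein preparations or immunological preparations (e.g., vaccines) should be avoided", and gives as the reason a possible unforeseen or heightened immune response. The Highlights repeat the advice: "Avoid simultaneous administration of ACTIMMUNE with other heterologous serum protein or immunological preparations (e.g., vaccines). (7.3").

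The protocol body does point to Appendix 16.2 in Section 6.1, but only when describing the approved indications: "ACTIMMUNE is approved for use in the US in patients with CGD and SMO (see prescribing information in" Section 16.2). Home dosing is covered in Section 8.4.7.3, where families are "instructed to administer study drug on an outpatient basis TIW (e.g., a dosing schedule of Monday, Wednesday and Friday" or a similar pattern). That section deals with technique, injection sites and schedule, not with vaccination.

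**The concern.** The section that is meant to carry medication restrictions says that there are none, while an appendix of the same protocol advises against a particular combination. A coordinator who is asked whether a subject may have a vaccine today will turn to 8.4.10, and the answer there is an unqualified yes, with nothing about keeping the injection apart from a study dose.

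The setting makes the question a realistic one. Subjects are children and young adults (the SAP's age bands in Section 7.3 begin at 10), treatment has no fixed end, and doses are given at home without staff present. That some subjects will be vaccinated during treatment is an assumption, since no rate is given, but it is a plausible one. The study's only objective is long-term safety.

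**Working it through.** The plan states no figure on this point, so the check is a comparison of texts, followed by simple arithmetic on the dosing schedule.

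**Comparison of the texts**

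| Place | Content on vaccines, immunological preparations or serum proteins |
|---|---|
| Protocol 8.4.10 | No medication restricted; no exception, no cross-reference |
| Protocol 8.3.1 and 8.3.2 (eligibility) | None; the exclusion criterion concerns disease or other conditions, judged by the investigator |
| Protocol 8.4.1.1 (dose adjustment) | None |
| Protocol 8.4.7.3 (administration at home) | None |
| Protocol 8.5.4.1 to 8.5.4.4 (visits) | None; medication use is asked about |
| SAP | None |
| Appendix 16.2, label Highlights and label 7.3 | Avoid simultaneous administration |

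Within the two documents, the precaution appears only in the reproduced label.

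**Can a site assume that the label governs where the body differs?** No, because the body departs from the label elsewhere:

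- Dose: the ceiling is 100 µg/m² (Section 8.4.1.1), against a label dose of 50 mcg/m². The ratio is 100/50 = 2, and label section 2.3 recommends against higher doses.
- Routine laboratory tests: every 6 months (Section 8.5.2.5), against every 3 months in label section 2.1.
- Injection sites: the abdomen is added (Section 8.4.7.3) to the deltoid and anterior thigh named in label section 2.2.

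A reader would reasonably take the protocol body as controlling. The dose ratio is listed only as an example of such a departure; the label does not link the vaccine precaution to dose.

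**Does monitoring prevent the event?** Medication use is asked about at contacts roughly 90 days apart. The number of home doses between contacts is 3 × 90/7 = 38.6, or about 39. The question records a vaccination after it has happened; it does not separate it from a dose.

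**What would separation cost?**

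- Dose-free days per week: 7 − 3 = 4.
- Planned doses in 26 weeks: 3 × 26 = 78. One skipped dose is 1/78 = 1.3%.
- Planned doses in 52 weeks: 3 × 52 = 156. One skipped dose is 1/156 = 0.6%.

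These figures measure the burden of the remedy, not the size of the risk.

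**The case against.** The best defence is that the advice is already in the protocol, twice, because the label is part of it. On this view the fault is a missing cross-reference, not missing information. The two texts can also be reconciled: label 7.3 bars no product, appears under Drug Interactions and not under Contraindications or Warnings, and concerns timing only, so it is still true that no medication is restricted.

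There are also channels that cannot be seen. Section 8.4.3 says that families receive separate dosing instructions. Section 11 has the sponsor brief sites about the drug and the Investigator Brochure passed to staff. Every subject has already had 26 weeks of the drug in HZNP-ACT-302 and may have been advised there. Finally, the label gives no incidence, severity or separation interval, so the harm is unquantified.

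Much of this stands as a limit on the claim. The precaution is about simultaneous use, its practical effect cannot be sized, and families may have been told by another route. It does not remove the conflict. A site reading 8.4.10 is given an unqualified rule and no reason to look in an appendix that the body cites only for the approved indications and departs from on other matters. Good separate instructions would still leave 8.4.10 at odds with the protocol's own appendix.

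**Conclusion.** The concern holds. Section 8.4.10 is a stated rule that conflicts with a labelled precaution reproduced in the same protocol, and nothing else in the protocol body or the SAP supplies that precaution. The consequence is for patient safety: vaccination at the same time as a dose is permitted as the section is written. No endpoint, summary or analysis is affected.

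The frequency and severity of any harm cannot be estimated from the documents. The practical importance rests on two assumptions: that some subjects are vaccinated during treatment, and that the unseen Investigator Brochure and dosing instructions do not already close the gap. The textual conflict depends on neither. It should be corrected, given how little the correction costs.

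**What to change.** Replace the second sentence of Section 8.4.10 with:

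> No concomitant medications are prohibited, except that study drug should not be given simultaneously with vaccines, other immunological preparations or heterologous serum proteins (see label section 7.3 in Appendix 16.2). Subjects and caregivers should contact the site before a planned vaccination so that doses can be timed apart.

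Repeat the second of these sentences in the home-dosing instructions in Section 8.4.7.3.

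The label names no separation interval, so the sponsor should either set one or leave it expressly to the investigator. Vaccinating on a day without a dose would, as an assumption, satisfy the label's wording.

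The cost is two sentences in 8.4.10, one in 8.4.7.3, and an occasional delayed or skipped dose. The SAP does not need to change.
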